#### 6.2.8. Follow-up Visit

**Subjects are required to fast for at least 9 hours prior to the visit.** Blood collection may be taken up to 48 hours following this visit as necessary to ensure samples are collected in a fasted state.

If a subject discontinues from or completes the study with abnormalities in hematology or clinical chemistry results which meet criteria as defined in Section 6.3.2, or a subject discontinues from the study due to an adverse event, a follow-up visit must be performed after the Early Termination study visit and at least 28 calendar days and up to 42 calendar days after last dose of study treatment. In addition, subjects who complete this study will have a follow-up visit at least 28 calendar days and up to 42 calendar days after the last administration of investigational product. The following procedures will be performed:

- Laboratory testing: Hematology, Chemistry Panel; Lipid Panel (fasting), Urine Pregnancy Test (for women of childbearing potential only);
- Risk factor check for venous thromboembolism (see Section 7.5.8);
- Contraception check: Confirm and document that proper contraception is being used;
- Adverse event reporting and concomitant medication use.

If abnormalities in hematology or clinical chemistry results are still observed at the follow-up visit, the subject must continue to be followed until the laboratory abnormality stabilizes or returns to baseline levels as approved by the Sponsor.

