# 6.3.1. Monitoring Criteria

The following laboratory abnormalities require prompt retesting, ideally within one week:

- Any single hemoglobin value that drops  $\geq 2 \text{ g/dL}$  (or  $\geq 20 \text{ g/L}$ ) below baseline;
- Absolute neutrophil count  $<1.2 \times 10^{9}/L$  ( $<1200/mm^{3}$ );
- Absolute lymphocyte counts  $<0.5 \times 10^9/L$  ( $<500/mm^3$ );
- Platelet count  $<100 \text{ x } 10^9/\text{L} (<100,000/\text{mm}^3);$
- Serum creatinine increase >50% OR an absolute increase in serum creatinine >0.5 mg/dL (or 44 μmol/l) over the average of the screening and baseline values;
- Any creatine kinase (CK) >5x ULN (repeat laboratory testing should also include cardiac troponin).

If the abnormality is confirmed after re-test, follow-up should be discussed with the Sponsor and frequency of monitoring increased. Confirmation should be done based upon central laboratory results, but local laboratory results will be acceptable, particularly if these may be done more promptly.

In case of potential DILI, repeat laboratory tests should be taken within 48 hours of awareness. See Section 8.4.2 Potential Cases of Drug-Induced Liver Injury.

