#### **Descriptive Summaries:**

In general, the data for all continuous endpoints will be summarized by time point and treatment sequence in tables containing descriptive statistics (n, mean, standard deviation (s.d.), standard error (SE) of the mean, minimum, 1st, 2nd (median) and 3rd quartiles and maximum) for baseline and change or percent change from baseline for those endpoints measured at baseline. The data for all binary endpoints will be summarized by treatment group and by time point in tables showing descriptive statistics: N, n (i.e., number of responders), response rate (%), standard error of the response rate, and 95% confidence interval (CI) based on normal approximation. If  $\hat{p}$  is the estimated response rate, then the 95% CI is calculated as

$$\hat{p} \pm z_{0.975} \sqrt{\frac{\hat{p}(1-\hat{p})}{N}},$$

where  $z_{0.975}$  is the 97.5th percentile of the standard normal distribution and *N* is the number of subjects evaluable for the endpoint at the time point. If the lower bound is calculated to be negative, it will be set to 0%; if the upper bound is calculated to be larger than 100%, it will be set to 100%. In case when response rate is 0 or 100%, standard error will be reported as "NA" and the 95% CI will not be reported. The displays described above for continuous and response-type endpoints will only use available data with no imputation. Therefore, the calculation of response rates will use the number of evaluable subjects as denominators.

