## Appendix 2. DEFINITION AND USE OF VISIT WINDOWS IN REPORTING

For reporting purposes, the following visit windows will be used for efficacy/PRO variables and for any safety displays that display by week/month. All observations regardless of on- or off-treatment will be used. For an endpoint that consists of multiple components, e.g., ACR50 and DAS28-3(CRP), the components should be collapsed first in the same visit window to derive the endpoint.

If two or more visits/observations fall into the same window, the visit/observation closest to the target day will be used in the analyses. If there is a tie, the later visit/observation will be used. However, for a subject who discontinues from the study early prior to the Month 6 visit and who does not have an observation within the Month 6 visit window, if two or more observations fall in the same visit window (i.e., a visit window prior to Month 6), then the latest observation (rather than the observation closest to the target day) within this visit window will be used in the analysis for that visit window.

Visit Label	Target Day	Definition [Day Window]
Screening		< Day 1
Baseline	Day 1	Last non-missing assessment on or before Day 1 and prior to first dose of study drug administration
Week 2	Day 15	Day 2 to Day 21
Month 1	Day 29	Day 22 to Day 42
Month 2	Day 57	Day 43 to Day 70
Month 3	Day 85	Day 71 to [Treatment Switch Day or Day 98, whichever is smaller]
Month 4	Day 113	[Treatment Switch Day + 1 or Day 99, whichever is smaller] to Day 140
Month 6	Day 169	≥ Day 141

Target day is equal to the target week  $\times$  7 days + 1 day. A month is 4 weeks or 28 days.

Treatment Switch Day = date of the first dose of treatment switch at month 3 (i.e., treatment switch date – date of the first dose + 1). The first dose of the treatment switch at Month 3 will be taken from the first dosing date from the Month 4 oral dosing CRF.

All the data collected on the treatment switch day will be counted in  $\leq$  Month 3 except for the AE data. Any new treatment emergent AE occurred on the day of treatment switch will be counted in  $\geq$  Month 4.

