Note that the upper limit of the Month 3 visit window and the lower limit of the Month 4 visit window are defined for each of ALL the subjects in the study since, per the study protocol, subjects randomized to the placebo group will receive tofacitinib 5 mg BID in a blinded fashion for the remainder of the study. Further details for the Month 3/Month 4 visit windows are in order.

PFIZER CONFIDENTIAL Page 41

- 1. If Treatment Switch Day falls between Day 71 and Day 98, then the upper limit of the Month 3 visit window is the smaller of Treatment Switch Day or Day 98 and the lower limit of the Month 4 visit window is the smaller of Treatment Switch Day + 1 or Day 99;
- 2. If Treatment Switch Day is < 71, > 98, or missing, the upper limit of the Month 3 visit window will be Day 98 and lower limit of the Month 4 visit window will be Day 99.

If Treatment Switch Day is < 71 71-98 > 98 Missing Visit label Month 3 Month 4 Month 4 Month 3 Month 4 Month 3 Month 3 Month 4 Day Window 71 to 98 99 to 140 71 to 98 99 to 140 71 to 98 99 to 140 from from [72 to 140] [71 to 71] up to up to [71 to 98] [99 to 140]

Effects of Bullets 1 and 2 above are further illustrated as follows.

The visit window definitions will be applied to all the endpoints, such as efficacy, PRO, safety etc. Note some of the endpoints may not be measured at every visit. For example, dactylitis will be assessed at baseline, Months 1, 3, and 6, and visit windows at Week 2, Months 2 and 4 will be undefined. In the event that an observation may fall into one of the undefined visit windows, that observation will not be used in analysis.

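### SAP Appendix 2 gives scheduled laboratory samples no priority, so a retest can displace the abnormal value that prompted it in by-visit tables (minor)

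*SAP*

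**What the plan says.** SAP Appendix 2 states that "the following visit windows will be used for efficacy/PRO variables and for any safety displays that display by week/month", and later that "The visit window definitions will be applied to all the endpoints, such as efficacy, PRO, safety etc". Within a window, "If two or more visits/observations fall into the same window, the visit/observation closest to the target day will be used in the analyses"; a tie goes to the later one. There is one exception. For a subject who discontinues before the Month 6 visit "and who does not have an observation within the Month 6 visit window", "then the latest observation (rather than the observation closest to the target day) within this visit window will be used". The appendix does not distinguish scheduled from unscheduled or repeat samples.

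Protocol 6.3.1 supplies the second sample: "The following laboratory abnormalities require prompt retesting, ideally within one week". The list covers hemoglobin, neutrophils, lymphocytes, platelets, creatinine and CK.

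SAP 6.6.2 plans change-from-baseline statistics by treatment group and visit for laboratory tests, plus categorical tables. SAP 5.2 describes general "tables containing descriptive statistics (n, mean, standard deviation (s.d.), standard error (SE) of the mean, minimum", with quartiles and maximum following. SAP 6.6 defers to CDISC and the sponsor's own reporting standards (CaPS), whose content is not in the documents.

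**The concern.** A retest under 6.3.1 exists only because the first value was abnormal. A selection rule that can prefer the retest is therefore not neutral: on average it moves the displayed value towards normal. Protocol 1.2.3 names falls in hemoglobin and neutrophils as changes associated, or potentially associated, with tofacitinib. The hemoglobin trigger is itself a change from baseline (a drop of at least 2 g/dL), which is the quantity tabulated by visit. If triggers are commoner on tofacitinib, the displayed contrast with placebo would narrow slightly.

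Months 1 and 2 matter most because they lie in the placebo-controlled period. Week 2 has no scheduled hematology or chemistry, and the Month 3 window normally closes on the switch day. Months 4 and 6 are exposed too, but by then both groups are on active drug.

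What can drop out of a row is mainly a single unconfirmed abnormal value. Protocol 8.2.2 says that repeating a test is not by itself enough to make the result an adverse event, so such a value need not appear in the adverse event tables either.

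**Working it through.** **Inputs.** Target days and reporting windows from SAP Appendix 2: Month 1 is Day 29 (Days 22-42) and Month 2 is Day 57 (Days 43-70). Visit windows from the Schedule of Activities: ±3 days at Month 1, ±7 days at Month 2. Retest timing from Protocol 6.3.1. I use lags of 1-7 days, and 4-10 days as a slower case (my assumption).

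**The plan's own figure.** Target day = week × 7 + 1, so 4 × 7 + 1 = 29 and 8 × 7 + 1 = 57. Both agree with the table.

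**General rule.** Let s be the scheduled draw day minus the target day, and r the lag to the retest. The retest is used if it lies in the window and |s + r| ≤ |s|.

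- If s ≥ 0, then s + r > s, so replacement never happens.
- If s < 0, the condition becomes r ≤ 2|s|.

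Counts of qualifying lags, from the earliest draw (largest |s|) to the day before target:

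| Lag | Month 1 | Month 2 |
|---|---|---|
| 1-7 days | 6+4+2 = 12 of 7×7 = 49 (24%) | 7+7+7+7+6+4+2 = 40 of 15×7 = 105 (38%) |
| 4-10 days | 3+1+0 = 4 of 49 (8%) | 7+7+7+5+3+1+0 = 30 of 105 (29%) |

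Among draws before the target day only, at 1-7 days: 12/21 = 57% and 40/49 = 82%.

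**Example.** The Month 2 visit is on Day 52 with ANC 1.1, below the 1.2 trigger. The retest on Day 58 is normal. The distances to Day 57 are 5 and 1, so the Month 2 row shows the retest.

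**Latest-value rule.** Any retest inside the window wins. At 1-7 days that is 49/49 at Month 1 and 104/105 at Month 2 (Day 64 + 7 = Day 71 falls outside). This applies only where both conditions of the exception hold.

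**Other windows.** Months 4 and 6 have ±7-day visits, so the general rule again gives 40/105 at 1-7 days. At Month 3, if the switch day is the visit day, a later retest falls in the Month 4 window. If the switch day is missing or outside Days 71-98, the Month 3 window runs to Day 98 and the count is again 40/105.

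**How many values.** The documents give no trigger rate. Assume 1%, 3% or 5% of an arm has a trigger for a given parameter at that visit, with visit days uniform over the visit window. Values replaced = rate × N × share. For N = 136:

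| Lag | Month 1 | Month 2 |
|---|---|---|
| 1-7 days | 0.33 / 1.00 / 1.67 | 0.52 / 1.55 / 2.59 |
| 4-10 days | 0.11 / 0.33 / 0.56 | 0.39 / 1.17 / 1.94 |

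For N = 68, halve these.

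**Effect on a mean.** For one replaced hemoglobin value that recovers by 1-2 g/dL (assumed), the shift is 1/136 to 2/136 = 0.007 to 0.015 g/dL on tofacitinib, or 1/68 to 2/68 = 0.015 to 0.029 g/dL on placebo.

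**The case against.** The strongest reply is that the deciding source is out of sight. The standards named in SAP 6.6 may keep unplanned samples out of by-visit tables, or may already include a worst-value table. Protocol 6.3.1 also accepts local-laboratory confirmation, and outside the COVID-19 provisions the documents do not say that local results enter the database. This stands, and it is why the point covers only retests that reach the analysis data. If the standards do exclude unplanned samples, Appendix 2 as written disagrees with them and still needs a line.

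It can also be said that the rule is pre-specified, identical in both arms and used only for descriptive output. Individual data review, the E-DMC, the hematologic events of special interest, the discontinuation criteria and the special attention promised in Protocol 9.4 all offer protection. This largely stands and keeps the point minor. But of the 9.4 commitment, SAP 6.6.1 carries over only anemia events, and SAP 6.6.2 names no worst-value laboratory table.

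Four stronger readings are tempting and not supported:

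- That 24% or 38% of patients are affected. These are shares of equally weighted day pairs, given a retest.
- That the latest-value rule loses the abnormality nearly every time. It replaces the value, but a retest that confirms the finding is itself abnormal. Most laboratory discontinuation criteria in 6.3.2 require two sequential breaches, so the row may still show one.
- That the categorical tables are distorted. SAP 6.6.2 does not make clear that they are by visit. Even if they are, a count changes only when the retest falls in a different category.
- That last-dose cut-off days can be set beyond which a follow-up sample enters the Month 6 window and restores the general rule. Protocol 6.2.8 says "a follow-up visit must be performed after the Early Termination study visit and at least 28 calendar days and up to 42 calendar days", counted from the final dose, while 6.3 and 6.3.2 give 28 days ±7. The protocol conflicts with itself, so no firm boundary follows.

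**Conclusion.** The gap in the text is real: the stated rule can swap a triggering laboratory value for its own retest in by-visit change-from-baseline rows, and the selection runs mainly towards normal. Where the SAP 5.2 statistics are used for laboratory data, a triggering value that was the minimum or maximum of its arm would also leave the row.

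The consequence is small. Under the assumed trigger rates, between about 0.1 and 2.6 values per parameter and visit would be replaced in the tofacitinib arm, and each moves an arm mean by hundredths of a g/dL at most. The true number cannot be found from the documents. The primary ACR50 analysis and the adverse event and special-interest summaries are untouched. This sits at the low end of minor and merits a change because the change is cheap.

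**What to change.** In SAP Appendix 2, add for by-visit laboratory displays: the sample from the nominal scheduled visit is used unless it is missing or documented as a laboratory error; only then is an unscheduled or retest value in the window used. The error clause matters, because absolute priority would keep a known bad result over its valid repeat. Where a valid scheduled sample exists, replacement falls to 0 of 49 and 0 of 105 day pairs.

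In SAP 6.6.2, add a summary of worst post-baseline values from all scheduled and unscheduled samples, Baseline to Month 3 by treatment group. If the sponsor standards already contain that table, cite it instead.

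The cost is two sentences in the SAP, plus a nominal-visit flag and a laboratory-error flag in programming. It needs no new data and no protocol amendment. The downside is that laboratory windowing will differ from efficacy windowing, which the appendix should state.

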## 7.5.2. Electrocardiogram

Twelve-lead electrocardiograms (ECGs) will be obtained on all subjects at the Screening and the Month 6 (or Early Termination) visit. All ECGs should be performed after the patient has rested quietly for at least 10 minutes. Screening visit ECG results will be used as a screening tool and should be maintained in the subject's source documentation. ECGs obtained at Month 6 will be compared to Screening ECGs. Any clinically significant changes from the Screening ECG will be recorded as adverse events and evaluated further, as clinically warranted.

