#### 6.6.2. Other Safety Summaries

For laboratory tests, 12-lead ECG parameters and vital signs, summaries include categorical tables (e.g., normal, high, low), and descriptive statistics for change from baseline by treatment group and visit. For the fluorescence-activated cell sorting (FACS), the endpoints to be summarized, which are subsets of lymphocytes and are measured at baseline, Month 3, and Month 6/early termination, are as follows: CD3 + (%, abs), CD3 + CD4 + (%, abs), CD3 + CD8 + (%, abs), CD19 + (%, abs), CD16 + /CD56 + (%, abs). Raw values as well as percent change from baseline will be summarized with descriptive statistics by treatment group and visit.

Demographic parameters will be summarized (as number and percent or mean, standard deviation, and range) by treatment group and gender following CaPS.

The number and percent of subjects reporting specific past and present medical histories at screening will be summarized by medical history reporting term (from the Medical Dictionary for Regulatory Activities (MedDRA)) and treatment group following CaPS.

Clinical findings on any physical examination during the study will be tabulated by treatment group following CaPS.

Previous and concomitant mediation usage by medication type will be tabulated by treatment group using the WHO-Drug dictionary following CaPS.

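### The visit-window rule in SAP Appendix 2 drops Early Termination ECGs before Day 141, and most Early Termination FACS and HbA1c results, from the by-visit safety summaries

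*SAP*

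**What the plan says.** **The window rule.** Appendix 2 of the SAP defines Baseline, Week 2 and Months 1, 2, 3, 4 and 6 by day ranges. There is no ET row, and Month 6 begins at Day 141. A window is undefined for a measure not scheduled at that visit; the SAP's example is dactylitis at Week 2 and Months 2 and 4. The consequence is stated outright: "In the event that an observation may fall into one of the undefined visit windows, that observation will not be used in analysis". The one provision for subjects who leave early picks the latest of several observations inside a window. It does not move an ET result to another visit.

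**Its reach.** Appendix 2 gives two statements of scope. It opens by saying the windows are "for efficacy/PRO variables and for any safety displays that display by week/month". It closes with: "The visit window definitions will be applied to all the endpoints, such as efficacy, PRO, safety etc".

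**What is collected and shown.** Protocol 7.5.2 says 12-lead ECGs "will be obtained on all subjects at the Screening and the Month 6 (or Early Termination) visit". The Schedule of Activities places FACS, HbA1c, lipids, hematology, chemistry and urinalysis at Month 6 and at ET. SAP 6.6.2 describes the FACS endpoints as ones "which are subsets of lymphocytes and are measured at baseline, Month 3, and Month 6/early termination" and then summarizes them by treatment group and visit. For laboratory tests, ECG and vital signs, the same section plans categorical tables and "descriptive statistics for change from baseline by treatment group and visit".

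**The concern.** The protocol collects an ET ECG and ET laboratory samples so that subjects who stop early contribute a last safety assessment. Followed as written, the SAP leaves many of these results without a row in the by-visit tables. ECG is the clearest case: Month 6 is its only defined post-baseline window, so the by-visit ECG summary holds only subjects observed on or after Day 141. For FACS, the SAP names a Month 6/early termination measurement time for which its own windows provide no label.

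Comparing safety and tolerability is a primary objective (protocol 2.1.1), and early leavers include those withdrawn for laboratory abnormalities or adverse events. The two scope statements add a practical problem, because two programmers could build different safety tables from the same text.

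**Working it through.** **1. The plan's own figures.** Appendix 2 gives target day = week × 7 + 1. Weeks 2, 4, 8, 12, 16 and 24 give Days 15, 29, 57, 85, 113 and 169, which match the table.

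**2. Window lengths before Month 6.** Week 2 is Days 2-21 (20 days), Month 1 is Days 22-42 (21), and Month 2 is Days 43-70 (28). Month 3 is Days 71-98 (28) when there is no switch day between Day 71 and Day 98, which includes subjects who leave before switching. With a switch on Day 85 it is Days 71-85 (15). Month 4 fills the rest to Day 140 (42 or 55). The total is 20 + 21 + 28 + 28 + 42 = 139 days.

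**3. Undefined days for an ET visit on Days 2-140.** Scheduled visits come from the protocol's Schedule of Activities and its footnote 7 (apolipoproteins).

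| Measure | Defined windows before Day 141 | Undefined days of 139 |
|---|---|---|
| ECG | none | 139 (100%) |
| FACS, HbA1c | Month 3 | 139 − 28 = 111 (80%); switch on Day 85: 139 − 15 = 124 (89%) |
| Apolipoproteins | Months 1, 3 | 139 − 21 − 28 = 90 (65%) |
| Standard lipid panel | Months 1, 3, 4 | 20 + 28 = 48 (35%) |
| Hematology, chemistry, urinalysis | Months 1, 2, 3, 4 | 20 (14%) |
| Vital signs, CRP | all | 0 |

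These are shares of calendar days, not of subjects. The apolipoprotein figure uses the Month 3 window to Day 98.

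**4. Approximate number of subjects.** The documents give no expected number or timing of early terminations, so this step is an assumption. Protocol 1.2.2 reports that 406 of 422 and 364 of 395 randomized subjects completed Month 3 in the two global studies. Dropout is then 16/422 = 3.8% and 31/395 = 7.8%. I assume a constant hazard over 84 days and that everyone attends ET.

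- Hazard h = −ln(1 − p)/84, which is 0.000460 or 0.000973 per day.
- Share leaving before Day 141 = 1 − exp(−139h), which is 6.2% or 12.6%. Times 204, this is 12.6 or 25.8 subjects, all with an unused ET ECG. At 2:1 that is about 8 to 17 on the tofacitinib sequence and 4 to 9 on the placebo sequence.
- FACS and HbA1c, low end (3.8%, Month 3 to Day 98; undefined Days 2-70 and 99-140): 204 × {[1 − exp(−69h)] + [exp(−97h) − exp(−139h)]} = 204 × (0.0313 + 0.0183) = 10.1.
- FACS and HbA1c, high end (7.8%, Month 3 to Day 85; undefined Days 2-70 and 86-140): 204 × {[1 − exp(−69h)] + [exp(−84h) − exp(−139h)]} = 204 × (0.0649 + 0.0480) = 23.0.

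The counts fall in proportion if fewer subjects attend ET: at 60% attendance, 12.6 × 0.6 to 25.8 × 0.6, or about 8 to 15 ECGs.

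**The case against.** **The loss is narrower than total exclusion.** A reader might infer that these results vanish from the safety report. The documents do not support that. The opening scope statement limits the windows to displays by week or month, SAP 6.6.2 lists categorical tables separately from the by-visit statistics, and SAP 6.6 sends laboratory and ECG summaries to sponsor standards that are not in these documents. The FACS phrase in 6.6.2 says when FACS is measured; it does not promise an ET display. This objection stands, and the point is confined to the by-visit summaries.

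**Other reporting catches the important cases.** Clinically significant ECG changes are adverse events (protocol 7.5.2), as are test results that lead to discontinuation (protocol 8.2.2). SAP 6.6.1 summarizes safety events that trigger withdrawal. Hematologic events including lymphopenia, hepatic events and renal events are of special interest (SAP Appendix 3, section 13). This also stands and is a large part of why the point is minor.

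**The ECG table is not a placebo comparison.** By Month 6 the remaining placebo-sequence subjects have switched to tofacitinib. A reader might infer a biased comparison with placebo, but the Month 6 ECG summary never offered one.

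**Replacement of on-drug by off-drug values.** Because "All observations regardless of on- or off-treatment will be used", a reader might infer that a dropped ET lipid result is systematically replaced by a post-treatment one from the follow-up visit. The documents do not establish this. Protocol 6.2.8 puts that visit "at least 28 calendar days and up to 42 calendar days after last dose of study treatment", but protocol 6.3, 6.3.2 and 7.5.7 give 28 ± 7 days for overlapping cases. At lags of 21 to 35 days, some follow-up visits after ET on Days 43-49 also land in the undefined Month 2 window. Early leavers need the visit only after an adverse event or a qualifying hematology or chemistry abnormality, and the last dose need not fall on the ET day.

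**Conclusion.** The gap is real but modest. The day counts follow from the text alone: in the by-visit summaries, every ET ECG before Day 141 is unused, as are ET FACS and HbA1c results on 111 to 124 of 139 days, apolipoproteins on 90, the standard lipid panel on 48, and hematology, chemistry and urinalysis on 20. ET results inside a defined window are kept.

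The subject counts (about 13 to 26 ET ECGs and 10 to 23 ET FACS or HbA1c results) rest on borrowed dropout rates, a constant hazard and full ET attendance. Nothing in the documents says how abnormal the omitted values would be, so I put no figure on the distortion of any table.

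A reader might extend the point to efficacy. The primary ACR50 analysis is unaffected because its components are assessed at every treatment visit and at ET, so all its windows are defined. Other efficacy results are nominal under SAP 5.1, and no change to them is proposed.

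**What to change.** Keep every window, and keep the discard rule for the scheduled-visit rows. Lifting the rule for safety data would push ET results into visits at which the measure was never scheduled.

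1. In Appendix 2 and SAP 6.6.2, add a separate descriptive Early Termination row for ECG, FACS, HbA1c, lipids (including apolipoproteins), hematology, chemistry and urinalysis. Split it into ET on or before the Treatment Switch Day, shown by treatment, and ET after it, shown by sequence. Subjects who leave without switching belong in the first part.
2. Footnote that an ET value inside a defined window also appears in that visit's row.
3. Reconcile the two scope statements in Appendix 2: the windows and the discard rule apply to by-visit displays only. Categorical safety tables not shown by visit include ET values, attributed to the treatment period in which they were collected.

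The cost is SAP wording and some extra table rows before database release. No new data are needed, and no existing row, efficacy result or primary analysis changes. The new rows will be small (at most about 8 to 17 tofacitinib-sequence and 4 to 9 placebo-sequence subjects under the assumptions above, before the split at the switch) and support description only.
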